However, most of these patients will eventually progress while on lenalidomide therapy. Patients with “symptomatic progression of disease (POD)” defined by new symptomatic bone lesions, progressive anemia, hypercalcemia, or progressive renal failure attributable to the multiple myeloma, usually in association with a rise in the serum or urine paraprotein, will require re-induction therapy with combination chemotherapy to prevent further organ deterioration. However, the subset of patients with “serologic or asymptomatic POD”, i.e. whose only evidence of disease progression is an increase in the paraprotein level by $\geq 25\%$ above plateau baseline, have a variable natural history with many patients not showing symptomatic progression for months. Based on the results of the initial phase I trial of lenalidomide in which higher responses were seen with higher doses of lenalidomide, we hypothesize that in patients relapsing on lenalidomide maintenance doses of 5-15 mg orally daily, the disease could be brought under control by increasing the dose of lenalidomide (intensification) to 25 mg. However, the response rates and tolerance of lenalidomide dose intensification in the setting of lenalidomide maintenance is unknown, which is the basis for the proposed clinical trial.

For the purpose of clarity, the term asymptomatic POD will be used henceforward to designate serologic only POD, while symptomatic POD will be used to designate POD associated with progression of organ damage.

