1.2 Study Design and Objectives

The proposed study is designed as a Phase II, multi-center trial of lenalidomide intensification in patients with asymptomatic POD while on low dose lenalidomide maintenance after HDM/ASCT or as continuous/maintenance therapy after initial treatment. The primary objective of this trial is to determine the overall response rate (ORR) at 6 months and the toxicity of lenalidomide administered at a dose of 25 mg orally, days 1 to 21 of a 28 day-cycle, without or with dexamethasone added after 2 cycles, in patients with multiple myeloma found to have asymptomatic POD while on a maintenance lenalidomide dose of 15 mg daily or less.

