4.0 OVERVIEW OF STUDY DESIGN/INTERVENTION

4.1 Design

In this multi-center Phase II single arm trial, 53 patients fulfilling the eligibility criteria, will be treated with lenalidomide 25 mg PO daily for 21 out of 28 day cycles. The patients' responses to the treatment will be assessed after every cycle. Patients who have asymptomatic POD after 2 cycles will have dexamethasone added at a dose of 40 mg PO weekly. Patients who have at least SD after 2 cycles will continue lenalidomide single agent until asymptomatic POD, at which time they will have dexamethasone added at a dose of 40 mg PO weekly. Patients will be taken off study if they have symptomatic POD after any cycle, if they have any type of POD after dexamethasone is added, or if they do not tolerate the treatment. The patients taken off study due to any type of POD, will be considered failures for the primary response endpoint if progression occurred within 6 months. Patients who are removed from study prior to completing 2 cycles of therapy for reasons other than POD will be considered inevaluable for response and will be replaced. Accrual will continue until 53 evaluable patients have been accrued. Patients who have received any study drug will be evaluated for safety.

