9.2.1. Instruction for Initiation of a New Cycle

A new course of treatment may begin on the scheduled Day 1 of a new cycle if:

- The ANC is $\geq 1,000/\mu\text{L}$
- The platelet count is $\geq 50,000/\mu\text{L}$
- Hemoglobin is $\geq 8\text{g/dL}$
- Any drug-related side effect rash, allergic reaction/hypersensitivity, sinus bradycardia/

**MEMORIAL SLOAN-KETTERING CANCER CENTER
IRB PROTOCOL**

IRB#: 11-107A(12)

other cardiac arrhythmia adverse event, dyspepsia, gastritis, gastric or duodenal ulcer or confusion or mood alterations that may have occurred has resolved to \leq grade 1 severity

- Any other drug-related adverse events that may have occurred have resolved to \leq grade 2 severity.

If these conditions are not met on Day 1 of a new cycle, the subject will be evaluated weekly and a new cycle of lenalidomide will not be initiated until the toxicity has resolved as described above. If the toxicity does not resolve after four weeks of delay, the patient will be taken off study.

If dosing of lenalidomide was halted during the previous cycle and was restarted with a one-level dose reduction without requiring an interruption for the remainder of the cycle, then that reduced dose level will be initiated on Day 1 of the new cycle.

If dosing of lenalidomide was omitted for the remainder of the previous cycle or if the new cycle is delayed due to toxicity newly encountered on the scheduled Day 1, then the new cycle will be started with dose modifications as described in Section 9.2.3.

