13.0 CRITERIA FOR REMOVAL FROM STUDY

Treatment with study drugs is to be discontinued when any of the following occurs:

- Symptomatic POD, i.e. *with organ damage* at any point in time during the treatment
- Asymptomatic POD, i.e. *without organ damage* after at least one cycle of lenalidomide and dexamethasone
- Adverse event(s) that, in the judgment of an Investigator, may cause severe or permanent harm or which rule out continuation of study drug

MEMORIAL SLOAN-KETTERING CANCER CENTER IRB PROTOCOL

IRB#: 11-107A(12)

- Major violation of the study protocol
- Withdrawal of consent
- Patient is lost to follow-up
- Suspected or confirmed pregnancy. If pregnancy or a positive pregnancy test does occur in a study subject or the partner of a male study subject during study participation, study drug must be immediately discontinued.

Any possible premature discontinuation would be documented adequately with reasons being stated, and information would have to be issued according to local requirements (e.g., IRB, regulatory authorities, etc.).

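### Treated patients who leave before 2 cycles without progression are dropped from the response rate and replaced, and no all-treated rate is planned beside it

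*Combined protocol and SAP*

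**What the plan says.** Section 4.1 sets the evaluability rule. Patients removed "prior to completing 2 cycles of therapy for reasons other than POD will be considered inevaluable for response and will be replaced". It then says: "Accrual will continue until 53 evaluable patients have been accrued". Progression within 6 months is treated differently: those patients stay in the denominator as failures.

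The reasons for removal include early toxicity. Section 4.1 takes patients off study "if they have any type of POD after dexamethasone is added, or if they do not tolerate the treatment". Section 9.2.1 adds: "If the toxicity does not resolve after four weeks of delay, the patient will be taken off study". Section 13.0 stops treatment for "Adverse event(s) that, in the judgment of an Investigator, may cause severe or permanent harm or which rule out continuation of study drug", and also for major protocol violation, withdrawn consent and loss to follow-up.

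An all-treated population exists for safety only: "Patients who have received any study drug will be evaluated for safety".

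Section 14.0 tests 15% against 30%, declares success at 12 or more responders among 53, and promises one response estimate with a confidence interval. It does not mention replacement, and it plans no response rate over all treated patients. Sections 1.6 and 14.0 both give 53 as the total to be accrued, and Section 7.0 divides 15 + 38 = 53 between the lead centre and the collaborating centres. Only Section 4.1 shows that more than 53 may be treated.

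**The concern.** Whether a patient counts towards the primary endpoint is decided after dosing has started, and partly by how the patient tolerates the drug. Someone who starts the intensified dose and stops for toxicity in cycle 1 leaves the response denominator, and another patient takes the place. The resulting rate describes patients who either got through 2 cycles or progressed.

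That matters here because Section 1.1 gives as the basis for the trial that "the response rates and tolerance of lenalidomide dose intensification in the setting of lenalidomide maintenance is unknown". A clinician deciding whether to intensify needs the chance of response among those who start. If early leavers respond less often than those who stay, the only rate the plan reports is too high for that purpose. A reader of Section 14.0 alone would also take 12/53 to be a result over every patient enrolled.

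**Working it through.** **Inputs.** From Section 14.0: null 15%, target 30%, both error limits 0.10, n = 53, cut-off 12, historical rates 12.5% to 16.4%. From Section 4.1: the replacement rule. The share of treated patients leaving before 2 cycles without progression, d, is not in the documents; 5% and 10% are illustrative. Section 3.1.3 reports 13% stopping for adverse events in a maintenance trial at 10 mg/day, but over that trial's whole follow-up and at a lower dose, so it does not estimate d.

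**Step 1: reproduce the design.** Exact binomial, with X the number of responders among 53:
- P(X ≥ 12 | 0.15) = 0.0907
- P(X ≥ 12 | 0.30) = 0.9094

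Both limits are met, and 53 is the smallest n that meets them. Cut-off 11 would give alpha 0.162, and cut-off 13 would give power 0.846. These error rates hold for the 53 evaluable patients.

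**Step 2: effect on the estimate.** With 12 responders and k replaced patients, none of whom responded, the all-treated rate is 12/(53 + k). Intervals are exact 95%.

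| Replaced | Share of treated | Rate | 95% CI |
|---|---|---|---|
| 0 | 0% | 12/53 = 22.6% | 12.3 to 36.2 |
| 3 | 3/56 = 5.4% | 12/56 = 21.4% | 11.6 to 34.4 |
| 6 | 6/59 = 10.2% | 12/59 = 20.3% | 11.0 to 32.8 |

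This step needs no assumption about the null. It does assume that replaced patients did not respond.

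**Step 3: chance of success at the 15% null, if 15% is an all-treated rate.** If leavers never respond, the rate among evaluable patients is 0.15/(1 − d):
- d = 5%: 0.15/0.95 = 0.158, so P(X ≥ 12) = 0.121
- d = 10%: 0.15/0.90 = 0.167, so P(X ≥ 12) = 0.162

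If leavers respond at half the null rate, 0.075, the evaluable rate is (0.15 − 0.075d)/(1 − d):
- d = 5%: 0.14625/0.95 = 0.154, so P(X ≥ 12) = 0.105
- d = 10%: 0.1425/0.90 = 0.158, so P(X ≥ 12) = 0.123

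If 15% is already an evaluable-patient rate, the value stays at 0.0907 whatever d is.

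**Step 4: separate the choice of null.** At a true rate of 16.4%, the top of the cited range, P(X ≥ 12) = 0.149 with nobody leaving. That excess comes from testing at 15%, not from replacement.

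**Step 5: price of changing the primary denominator.** Suppose the 12-of-53 rule is applied to the first 53 treated, 30% was meant for evaluable patients, and leavers do not respond. The true all-treated rate is then 0.30(1 − d):
- d = 5%: 0.285, power 0.865
- d = 10%: 0.27, power 0.806

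If both 15% and 30% are all-treated rates, alpha is 0.091 and power 0.909, as in Step 1.

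**The case against.** The rule is explicit, set in advance and narrow. Progression is never excused, and nothing in Section 4.1 drops patients who leave after 2 cycles. It touches response only: everyone dosed is assessed for safety, and no such exclusion is stated for progression-free or overall survival, so early intolerance is not hidden. Exits may be few. Patients enter already taking lenalidomide, those with prior severe events at higher doses that preclude an increase are excluded (Section 6.2), and there are four reduced dose levels before discontinuation (Section 9.2.3) and up to four weeks of delay. The shifts in Step 2 are small against an interval of 12.3 to 36.2. An evaluable-patient rate is a legitimate quantity, and counting withdrawn consent or loss to follow-up as non-response can bias activity downwards. A replaced patient could also have been an early responder.

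All of this stands, and it is why the primary analysis can stay as it is. None of it explains why the all-treated rate is missing.

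Two stronger readings are tempting but not supported. A reader might infer from Section 1.2, whose primary objective is "to determine the overall response rate (ORR) at 6 months and the toxicity of lenalidomide", that toxicity is settled as part of the primary objective and so must enter the primary rate. Section 2.0 lists toxicity as secondary, and Section 14.0 gives response alone as primary. A reader might also infer that the plan leaves the primary denominator unknown. Section 14.0 is silent, but read with Section 4.1 the 53 are evaluable patients. What remains open is which denominator lies behind 15%, 30% and the historical rates.

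**Conclusion.** The point holds as a reporting gap that should be fixed. The planned rate is conditional on not leaving before 2 cycles for a reason other than progression. It overstates the rate among all who start the intensified dose if early leavers respond less often. On illustrative counts of 3 or 6 replaced non-responders, 22.6% becomes 21.4% or 20.3%. The true size depends on an early exit rate that the documents do not give.

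A reader might infer that replacement breaks the trial's 10% type I error. The documents do not support that. For evaluable patients alpha stays 0.091 and power 0.909. The rise at the 15% null to 12.1% or 16.2% needs two assumptions the documents do not confirm: that 15% is an all-treated rate, and that leavers never respond. With leavers at half the null rate, the figures are 10.5% and 12.3%. The excess at 16.4% belongs to the choice of null.

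**What to change.** Keep 53 evaluable patients and the 12-responder rule.

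1. Add to Section 14.0, cross-referenced in 4.1, a response rate with an exact confidence interval over all patients who received any study drug. Count early leavers without a documented response as non-responders. Report it beside the evaluable rate, with the number replaced and the reasons.
2. State in Section 14.0 that the 53 are evaluable patients, and reconcile the total of 53 accrued in Sections 1.6 and 14.0 with accrual to 53 evaluable in Section 4.1.
3. State in Section 14.0 which denominator 15% and 30% refer to.

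These are wording changes using data already collected. They add no patients and leave alpha and power unchanged; the added rate may be lower than the evaluable one.

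Making the first 53 treated patients the primary denominator is optional. It changes the question being answered, and under the assumptions in Step 5 power falls to 0.865 or 0.806.

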4.2 Intervention

Patients with asymptomatic POD while on maintenance lenalidomide after HDM/ASCT or on continuous/maintenance therapy after initial treatment will be enrolled on this clinical trial and will undergo the following interventions:

- Patients will have their disease fully reassessed in order to establish a new pre-therapy baseline within 2 weeks of initiation of treatment.
- Patients will receive lenalidomide at a dose of 25 mg PO daily for 21 days out of 28-days-cycles.
- Patient will be evaluated for response and toxicity after every cycle.
- Patients with at least SD after 2 cycles of lenalidomide will continue on lenalidomide until asymptomatic POD, at which time dexamethasone will be added at a dose of 40 mg PO weekly at the next cycle.

MEMORIAL SLOAN-KETTERING CANCER CENTER IRB PROTOCOL

IRB#: 11-107A(12)

[figure not shown]
- Patients with asymptomatic POD after 2 or more cycles of lenalidomide will have dexamethasone added to lenalidomide at a dose of 40 mg PO weekly at the next cycle.
- Patients with further asymptomatic POD after at any cycle of lenalidomide and dexamethasone will be taken off study and treated at the discretion of the treating physician. Note that further POD after the addition of dexamethasone will be determined compared to the new M spike baseline just prior to the addition of dexamethasone.
- Note that patients with symptomatic POD at any point in time during treatment will be taken off study.

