1.5 Outcome Measurements

The response to treatment intervention will be measured using a modified version of the widely accepted Uniform International Response Criteria in multiple myeloma. To determine response, patients' disease will be assessed at the beginning of every cycle and compared to the new baseline established within two weeks prior to initiation of lenalidomide intensification.

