9.0 TREATMENT/INTERVENTION PLAN

9.1 Treatment Plan

- Lenalidomide dose will begin at 25 mg PO daily for 21 days of a 28-day-cycle adjusted for toxicity, if necessary. Once the dose of lenalidomide is reduced for toxicity, no dose-re- escalation is permitted.
- If a dose of lenalidomide is missed, it should be taken as soon as possible on the same day. If it is missed for the entire day, it should not be made up.
- Patients taking more than the prescribed dose of lenalidomide should be instructed to seek emergency medical care if needed and contact study staff immediately.
- Only one cycle of therapy may be dispensed to the patient each month. Lenalidomide capsules should be swallowed whole, and should not be broken, chewed or opened.
- Special Handling Instructions: Females of childbearing potential should not handle or administer lenalidomide unless they are wearing gloves.
- Record of administration: Accurate records will be kept in the source documents of all drug administration (including prescribing and dosing). Patients will be instructed to bring their complete medication diary (refer to Appendix D) to each study visit for assessment of compliance.

MEMORIAL SLOAN-KETTERING CANCER CENTER IRB PROTOCOL

IRB#: 11-107A(12)

- Patient will be evaluated for response and toxicity after every cycle and the response to lenalidomide intensification will be assessed after every cycle of therapy.
 - Patients with at least SD after 2 cycles of lenalidomide will continue on lenalidomide until asymptomatic POD at which time dexamethasone will be added at a dose of 40 mg PO weekly for the next cycle.
 - Patients with asymptomatic POD after 2 cycles of lenalidomide will have dexamethasone added to lenalidomide at a dose of 40 mg PO weekly with the next cycle.
 - Patients with further asymptomatic POD after any cycle of lenalidomide and dexamethasone will be taken off study and treated at the discretion of the treating physician. Note that further POD after the addition of dexamethasone will be determined compared to the new M spike baseline just prior to the addition of dexamethasone.
- Once patients are started on dexamethasone, they will also receive prophylaxis medication including Bactrim DS, one tablet PO TIW, fluconazole, 100 mg PO Daily, ASA 81 mg PO daily, and a PPI.
- Note that patients with symptomatic POD at any point in time during treatment will be taken off study.

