11.2 Expected Side Effects of Dexamethasone

Likely

- Increased appetite
- Weight gain
- Sleep disturbance
- Hypertension
- Fluid retention, ankle swelling
- Bruising
- Susceptibility to Infection
- Mood changes
- Slow wound healing
- Depression
- Hyperglycemia, which may lead to fatigue, weight loss, excessive thirst and frequent urination.

Less Likely

- Loss of appetite
- Muscle twitching
- Increased thirst, frequent urination
- Increased perspiration
- Diarrhea
- Nausea
- Headache
- Bone thinning
- Spinal fracture or fracture of bones
- Tachycardia
- Fungal infections

MEMORIAL SLOAN-KETTERING CANCER CENTER
IRB PROTOCOL

IRB#: 11-107A(12)

- Anxiety

Unlikely

- Blurred vision
- Personality changes
- Hypokalemia
- Swelling and/or redness of skin
- Allergic skin reactions
- Itching
- Hirsutism
- Muscle weakness or loss of muscle mass
- Rupture of tendons
- Menstrual cycle disturbances
- Facial puffiness, leading to the appearance of a “moon face” hormonal disturbances
- Hiccups.
- Development of diabetes

Rare but serious

- Stomach ulcers with bleeding that may cause hematemesis, blood in the stool and abdominal pain.
- Bowel perforation, irritation and bleeding of the esophagus
- Heart failure
- Allergic reaction that may lead to shortness of breath, abdominal cramps and hypotension
- Convulsions, brain swelling,
- Cataracts
- Glaucoma and increased blood pressure in the eye
- Pancreatic inflammation, abdominal swelling
- DVT or PE
- Aseptic necrosis of the hip

**12.0 CRITERIA FOR THERAPEUTIC RESPONSE/OUTCOME
ASSESSMENT**

Patients enrolled in this trial must have *asymptomatic* progression of disease only. The new baseline that will be used for comparison to assess the response to lenalidomide intensification with or without the addition of dexamethasone at 6 months will have to be established within two weeks prior to day 1 of cycle 1. Prior values will not be acceptable.

Patients' disease status at each data collection period will be evaluated based on the International Uniform Response Criteria. All disease responses, including after addition of dexamethasone, will be relative to the established baseline disease status within 2 weeks prior to day1 of cycle 1, i.e. prior to lenalidomide intensification.

MEMORIAL SLOAN-KETTERING CANCER CENTER
IRB PROTOCOL

IRB#: 11-107A(12)

International Uniform Response Criteria (modified)

Stringent Complete Response (sCR):

- sCR requires, in addition to CR (defined below), all of the following:

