- Patients who do not meet criteria for sCR, CR, VGPR, PR or progressive disease are considered to have stable disease (SD).

Progressive Disease (POD) requires one or more of the following:

- $>25\%$ increase in the level of the serum monoclonal paraprotein, which must also be an absolute increase of at least 0.5 g/dL.
- $>25\%$ increase in 24-hour urine protein electrophoresis, which must also be an absolute increase of at least 200 mg/24 hours.
- $>25\%$ increase in the difference between involved and uninvolved FLC levels (absolute increase must be >10 mg/dl),
- $>25\%$ increase in plasma cells in a bone marrow aspirate or on trephine biopsy, which must also be an absolute increase of at least 10%.
- Definite increase in the size of existing bone lesions or soft tissue plasmacytomas.
- Development of new bone lesions or soft tissue plasmacytomas.
- Development of hypercalcemia (corrected serum Ca >11.5 mg/dL or >2.8 mmol/L) not attributable to any other cause.

Note that the development of a compression fracture does not exclude continued response and may not indicate progression.

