14.0 BIOSTATISTICS

The primary objective of this study is to estimate overall response rate (\geq PR) to lenalidomide intensification with or without dexamethasone at 6 months. A single stage design that differentiates between response rates of 15% and 30% will be used to assess efficacy of lenalidomide intensification with or without dexamethasone.

The probabilities of a type I error (falsely accepting a non-promising therapy) and type II error (falsely rejecting a promising therapy) are set to 0.10 and 0.10, respectively. The null hypothesis response rate is based on the response rates ranging from 12.5% to 16.4% to the standard of care therapy in patients previously exposed to thalidomide who have relapsed or refractory disease (reference Webber and Dimopoulos papers^{38,39}). A total of 53 patients will be accrued. At the conclusion of the study, if a least 12 of the 53 patients respond by 6 months the treatment will be declared a success. At the end of the study, the response rate will be estimated and a confidence interval will be constructed.

We expect to accrue 53 patients in two years with approximately 10-15 patients accrued from MSKCC and the remaining patients accrued from the other centers.

The incidence of toxicities of grade 2 or higher toxicities (CTCAE version 4.0), the incidence of probable viral fungal and bacterial infections, and the incidence of treatment-related mortality, i.e., from causes other than relapse or progression, will be recorded for each patient after each cycle and at the end of study visit. Safety data will be described in a variety of ways, both graphically and in tabular form.

Progression free survival is defined as the time from treatment initiation to relapse/progression, death, initiation of non-protocol anti myeloma therapy, or last follow-up. Overall survival is defined as time from treatment initiation until death or last follow-up. Progression free and overall survival will be estimated using the Kaplan-Meier method.

We will estimate the response rate (CR, VGPR, and PR) by 6 months from initiation of lenalidomide intensification of lenalidomide given as single agent. For this calculation, patients who have asymptomatic progression after 2 cycles of lenalidomide and receive dexamethasone will be considered failures.

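### No rule measures POD from the lowest marker value reached, so a marker-only relapse after a response is called late and PFS in responders is overstated

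*Combined protocol and SAP*

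**What the plan says.** **After dexamethasone.** Section 4.2, repeated in 9.1, sets the reference: "further POD after the addition of dexamethasone will be determined compared to the new M spike baseline just prior to the addition of dexamethasone".

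**On lenalidomide alone.** Section 1.5 has disease assessed each cycle and "compared to the new baseline established within two weeks prior to initiation of lenalidomide intensification". Section 12.0 adds: "All disease responses, including after addition of dexamethasone, will be relative to the established baseline disease status within 2 weeks prior to day1"; the day meant is the start of the first cycle. Both sentences are about response. The POD list in Section 12.0 asks, for serum, for a more than 25% "increase in the level of the serum monoclonal paraprotein, which must also be an absolute increase of at least 0.5 g/dL", and does not say from which value.

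**Lost response.** Section 12.0 has no category for it: "Patients who do not meet criteria for sCR, CR, VGPR, PR or progressive disease are considered to have stable disease (SD").

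**What POD controls.** It decides when dexamethasone starts (9.1: "Patients with at least SD after 2 cycles of lenalidomide will continue on lenalidomide until asymptomatic POD at which time dexamethasone will be added") and when study drug stops (13.0). It is also a PFS event. Section 14.0 reads: "Progression free survival is defined as the time from treatment initiation to relapse/progression, death, initiation of non-protocol anti myeloma therapy". The list there closes with the date a patient was last followed. PFS is a secondary objective in 2.0 and is to be estimated by Kaplan-Meier.

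**Background.** Section 1.1 describes serologic POD differently, as a rise of at least 25% "above plateau baseline, have a variable natural history with many patients not showing symptomatic progression for months".

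**The concern.** Both named references are high values. The cycle-1 value is taken when the patient is already progressing, and the pre-dexamethasone value is taken at the next POD. A responder whose marker climbs again has to pass one of these high values by more than 25% and by at least 0.5 g/dL before the rise counts. Until then a patient who has lost a PR is classed as SD.

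Three things follow for marker-only relapse. The PFS date is late, and most so after the deepest responses. Dexamethasone may be added late. Removal from a failing combination may be late.

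This is likely to be the usual kind of relapse here. In the sponsor's own series (3.2.2.2), 14 of 16 relapses were first seen on immunofixation (4), SPEP (5) or free light chains (5), and 2 came to light through symptoms.

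**Working it through.** **The plan's own figure.** An exact binomial check of at least 12 responses in 53 gives type I error 0.0907 at 15% and power 0.9094 at 30%. The stated design reproduces, and nothing below changes it.

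**Threshold.** From Section 12.0, serum POD for a reference r lies at T(r) = max(1.25r, r + 0.5) g/dL. Where the 25% term governs, the value must be exceeded. Write b for the cycle-1 value and n for the lowest value.
- From the lowest value: T(n).
- Lenalidomide alone, if the cycle-1 value is the reference: T(b).
- After dexamethasone, if it was started at T(b): T(T(b)).

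The delay in marker doublings is log2 of the threshold ratio. The values of b and n are assumptions, because the documents give no M-protein distribution.

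| b | n | T(n) | T(b) | T(T(b)) | Doublings, lenalidomide alone | Doublings, after dexamethasone |
|---|---|---|---|---|---|---|
| 0.5 | 0.25 | 0.75 | 1.0 | 1.5 | 0.415 | 1.000 |
| 1.0 | 0.5 | 1.0 | 1.5 | 2.0 | 0.585 | 1.000 |
| 2.0 | 1.0 | 1.5 | 2.5 | 3.125 | 0.737 | 1.059 |
| 3.0 | 1.5 | 2.0 | 3.75 | 4.6875 | 0.907 | 1.229 |
| 4.0 | 2.0 | 2.5 | 5.0 | 6.25 | 1.000 | 1.322 |
| 2.0 | 0.2 | 0.7 | 2.5 | 3.125 | 1.837 | 2.158 |

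**Months.** Assume a regrowth doubling time of 3 months (range 2 to 6).
- Patient who just reaches PR, lenalidomide alone: 1.2 to 3.0 months (0.8 to 6.0 over the range).
- Same patient after dexamethasone: 3.0 to 4.0 months (2.0 to 7.9).
- After a 90% fall from 2.0 g/dL: 5.5 and 6.5 months (3.7 to 13.0).

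**Does the post-dexamethasone result depend on the lenalidomide-alone reading?** Suppose POD on lenalidomide alone is already taken from the lowest value. With b = 2.0 and n = 1.0, dexamethasone then starts at 1.5. If the marker falls back to 1.0, the written rule gives further POD at T(1.5) = 2.0, against T(1.0) = 1.5 from the lowest value. The delay shrinks to log2(2.0/1.5) = 0.415 doublings but does not vanish.

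**Effect on PFS.** This is an illustrative cohort of 400,000 simulated patients, and every input is assumed.
- Baseline: lognormal, median 1.0 g/dL, log SD 0.6, clipped to 0.5 to 5.
- Responders (30%): fall uniform on 50 to 90%, regrowth from 4 months plus an exponential time with median 4 months.
- Non-responders: exponential time to POD, median 4 months.
- Event: the first POD, so only the lenalidomide-alone reference enters.

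| Doubling time (months) | Responder median PFS, months: lowest vs cycle-1 | 12-month PFS, all patients: lowest vs cycle-1 | Overall median, months: lowest vs cycle-1 |
|---|---|---|---|
| 2 | 11.2 vs 13.1 | 22% vs 27% | 6.8 vs 7.2 |
| 3 | 12.9 vs 15.8 | 26% vs 34% | 7.0 vs 7.2 |
| 6 | 17.8 vs 23.6 | 35% vs 39% | 7.2 vs 7.2 |

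**Sensitivity.** With 15% responders and a 3-month doubling time, the 12-month gap is about 4 points. Adding a competing exponential event (assumed median 24 months) to the 30% cohort leaves a 12-month gap of about 3 to 5 points and moves the overall median by 0.01 month or less.

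**The case against.** A reader might infer that a relapsing responder has no POD and no PFS event at all until the old high value is passed. The documents do not support that. New or enlarging bone lesions or plasmacytomas and hypercalcemia are POD at any marker level, and death or non-protocol therapy also ends PFS. The point holds for marker-only relapse.

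A reader might also infer that the plan rules out the lowest value on lenalidomide alone. It does not say so. The baseline sentences in 1.5 and 12.0 concern response, and 6.1 and Appendix A defer to consensus criteria. Section 1.1 describes serologic POD against a plateau and then adopts the term asymptomatic POD for it, so a plateau reference could be read into 9.1. For this phase the defect is an unstated reference, with the cycle-1 value as the only baseline on offer. None of this rescues the post-dexamethasone rule, which is explicit.

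The cohort figures rest on the inferred phase, because they date PFS at the first POD. The explicit rule moves PFS only if the event is the off-study POD, which the plan leaves open. It governs removal either way.

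The effect is also modest. PFS is descriptive in one arm, the shortest delay (0.8 month) is under one 28-day cycle, and urine and FLC relapses were not quantified. All of this stands, and it limits the size of the point.

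Finally, earlier POD is not free. Section 4.1 counts off-study POD within 6 months as primary failure, and Section 14.0 counts patients who progress and receive dexamethasone as single-agent failures. The fix has to deal with both.

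**Conclusion.** The point stands in limited form. After dexamethasone the plan states a reference that dates marker-only relapse late in a patient who responded. On lenalidomide alone it states none, and the one baseline available would have the same effect. The thresholds (1.5, 2.5 and above 3.125 g/dL in the example) follow from Section 12.0 once b and n are chosen. For the 3.125 figure, dexamethasone must also have started at 2.5.

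PFS in responders is overstated. With the cycle-1 value as reference and the assumed cohort, the responder median is 1.9 to 5.8 months longer (13.1 − 11.2; 23.6 − 17.8) and 12-month PFS in all patients is 4 to 8 points higher. The overall median moves by 0.0 to 0.4 month, because most patients do not respond. The working does not support a claim that the trial's median PFS is materially wrong, or that the 12-of-53 decision is affected. A clarification before analysis is worthwhile; the design does not need to change.

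**What to change.** **Section 12.0.** Keep response against the cycle-1 baseline and add a POD reference for serum M-protein, 24-hour urine M-protein and the FLC difference, with the existing percentages and absolute minimums:
- on lenalidomide alone, the lowest value since the cycle-1 baseline, that baseline included;
- after dexamethasone, the lowest value since the pre-dexamethasone assessment, that assessment included.

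Require confirmation on a repeat measurement, both of the lowest value and of the rise, so that one stray reading cannot create a POD. Because the pre-dexamethasone value is included, nobody is removed for the POD that triggered dexamethasone. Where the lowest value is zero after a CR, let the absolute minimum alone apply.

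**Sections 2.0 and 14.0.** End PFS at the first such POD, any other POD listed in Section 12.0, death or non-protocol therapy.

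**Sections 4.2 and 9.1.** The sponsor can leave the treatment rules as they are and use the new reference for PFS only, which leaves both response endpoints untouched. If the rules for adding dexamethasone and for removal are changed too, state that a response already reached by 6 months still counts for the 12-of-53 rule when the new reference has merely brought the POD forward. Settle the single-agent response rate in 14.0 the same way.

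**Cost.** Wording changes. The markers are already measured before every cycle (10.1), the next pre-cycle sample can serve as the repeat, and POD dates for patients already treated can be recomputed from stored values. Reported PFS in responders will be slightly shorter. If the treatment rules change, some responders will receive dexamethasone or leave the study earlier.
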